Using underneath criteria patients will be included or excluded from this retrospective study. We estimate a sample size of 400 subjects within our department (UZ Leuven). Another 900 subjects are estimated to be included from the retrospective dataset provided by prof. [name] (King's College).

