3.2 Exclusion criteria

- Neuropathic pain in another region than the trigeminal nerve
- Neuropathic pain not caused by iatrogenic injury

4. Direct access to source data and documents

The selected CRF platform, CastorEDC (www.castoredc.com), permits trial-related monitoring, audit and EC review or regulatory inspection. Source data will be directly accessible to the rightful instance or person on request.

The trial will be conducted in compliance with the principles of the Declaration of Helsinki (current version), the principles of GCP and in accordance with all applicable regulatory requirements. This protocol and related documents will be submitted for review to the Ethics Committee.

The Investigator and the Participating Site shall treat all information and data relating to the Study disclosed to Participating Site and/or Investigator in this Study as confidential and shall not disclose such information to any third parties or use such information for any purpose other than the performance of the Study. All medical data, the data collected in the course of the study is treated with the utmost confidentiality. The medical secrecy, the international guidelines (ICH-GCP) and the Belgian legislation are complied with. The investigators undertake to respect the conditions in the European General Data Protection Regulation (2016/679 Europese Algemene Verordening Gegevensbescherming, AVG/GDPR) and the Belgian legislation on the protection of natural persons with regard to the processing of personal data.

5. Data Handling

Data will be analyzed by [name], statistician at Leuvens Biostatistiek en Statistische Bioinformatica Centrum. Following statistical methods will be applied.

Non-parametric analyses (Mann-Whitney U tests, Kruskal-Wallis tests, Spearman correlations, Fisher exact tests) will be used to compare in a univariable setting the primary and secondary endpoints between groups (e.g. type of nerve) and to evaluate relations between continuous and/or ordinal variables.

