(Multivariable) Linear models will be used to evaluate the relations with healthcare costs. In case the period referring to the calculation of the cost differs between subjects, a weighted version of the proposed model will be considered (with the weight being a function of the length of the period. The productivity loss (number of days) will be evaluated with (multivariable) models for count data (e.g. negative-binomial) will be used (with an offset term in case the periods differ between subjects). (Multivariable) logistic regression will be used for the permanent/temporary classification of the injury. In all multivariable models, multiple imputation methods based on the fully conditional specification (FCS) approach (8) will be considered to handle the presence of missing data. In models applied on aggregated data from Belgium and UK, center will be added as a fixed effect and it will be verified if the relations are country dependent.

P-values smaller than 0.05 will be considered significant. Given the multitude of planned analyses, a single significant p-value will be interpreted with caution.

6. Data Management

All medical data, the data collected in the course of the study is treated with the utmost confidentiality. The medical secrecy, the international guidelines (ICH-GCP) and the Belgian legislation are complied with. The investigators undertake to respect the conditions in the European General Data Protection Regulation (Europese Algemene Verordening Gegevensbescherming, AVG) and the Belgian legislation on the protection of natural persons with regard to the processing of personal data.

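### Merged Leuven and UK comparisons of symptoms, sensory tests, imaging and treatment by cause and nerve use tests without centre, and may be confounded by centre

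*Combined protocol and SAP*

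**What the plan says.** All references are to the combined protocol and SAP.

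- **Tests.** Section 5 (Data Handling) states: "Non-parametric analyses (Mann-Whitney U tests, Kruskal-Wallis tests, Spearman correlations, Fisher exact tests) will be used to compare in a univariable setting". They cover the primary and secondary endpoints, compared between groups such as nerve type. No stratified version is named.
- **Models.** The same section names a linear model for costs, a count model for productivity loss and a logistic model for permanent versus temporary injury. It then says: "In models applied on aggregated data from Belgium and UK, center will be added as a fixed effect". A check of whether relations depend on country is added, again for models.
- **What is merged.** Section 2.1 merges the UK dataset with the Leuven one to study presentation, symptoms, examination, radiology, treatment and outcome. Costs, medication use, productivity loss and EQ5D are restricted to Leuven records.
- **Numbers.** Section 3 expects 400 patients from Leuven and says: "Another 900 subjects are estimated to be included from the retrospective dataset".
- **Threshold.** "P-values smaller than 0.05 will be considered significant" (section 5; sidedness is not stated).

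**The concern.** The plan accepts that centre matters when the two datasets are pooled, but acts on it only in regression models. Of the three named models, costs and productivity loss use Leuven data alone, so only the logistic model can run on merged data.

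Secondary endpoint 2 (section 2.3) compares symptoms, pain descriptors, sensory testing and treatment by cause and nerve branch. No model is named for these comparisons, and the unstratified test stands alone. Imaging, which is also within the merged scope, is in the same position.

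The patients come from two referral centres in two countries. If one centre sees relatively more lingual nerve injuries and also records a symptom more often, a pooled test can show a nerve effect that exists in neither centre. With the opposite pattern it can hide a real one. Merging is justified in section 2.1 by shared eligibility criteria and a shared period. That does not establish equal case mix or equal measurement.

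**Working it through.** The plan gives no error-rate or power figure to reproduce; 400 and 900 are expected record counts. The check asks how a pooled test behaves when no group effect exists within either centre.

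**Inputs**
- From section 3: Leuven N = 400, UK N = 900, total 1300 (Leuven 400/1300 = 30.8%).
- From the background, earlier Leuven cohort of 53: lingual nerve share 21/53 = 40%; persistent disturbance 60%, used here only as a plausible level for a binary endpoint.
- From section 5: alpha 0.05, taken as two-sided.
- Assumed: all UK values. They are not in the documents and were varied.

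**Spurious difference, binary endpoint.** With no effect within centres,

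pooled difference = (UK rate − Leuven rate) × (UK fraction of group 1 − UK fraction of group 0).

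If either factor is zero, there is no bias.

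- UK share 50%, UK rate 50% (10 points each): group 1 has 160 + 450 = 610 patients and group 0 has 240 + 450 = 690. Difference = −0.10 × (450/610 − 450/690) = −0.10 × 0.0855 = −0.9 points.
- UK share 60%, UK rate 40% (20 points each): groups of 700 and 600. Difference = −0.20 × (540/700 − 360/600) = −0.20 × 0.1714 = −3.4 points.
- UK share 70%, UK rate 30% (30 points each): groups of 790 and 510. Difference = −0.30 × (630/790 − 270/510) = −0.30 × 0.2681 = −8.0 points.

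**False-positive rate, binary endpoint.** Pooled Fisher was set against Cochran-Mantel-Haenszel stratified by centre, with 2,000 runs per setting. At a true 5% the simulation standard error is √(0.05 × 0.95/2000) = 0.5 points.

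| Mix difference | Endpoint difference | Fisher, pooled | CMH by centre |
|---|---|---|---|
| only one of the two differs | (5 to 30 points) | 4.0-5.6% | 4.1-5.8% |
| 10 points | 10 points | 5.9% | 5.2% |
| 20 points | 10 points | 8.9% | 4.0% |
| 20 points | 20 points | 22.0% | 5.4% |
| 30 points | 20 points | 46.2% | 5.1% |
| 30 points | 30 points | 82.6% | 5.0% |

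**False-positive rate, continuous endpoint.** Pooled Mann-Whitney was set against van Elteren (within-centre ranks, weight 1/(N_c + 1)), with 1,500 runs per setting.

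| Mix difference | Centre shift | Mann-Whitney, pooled | van Elteren |
|---|---|---|---|
| none | 0.5 SD | 5.1% | 5.1% |
| 10 points | 0.25 SD | 5.9% | 4.3% |
| 10 points | 0.5 SD | 12.9% | 6.1% |
| 20 points | 0.25 SD | 11.5% | 5.3% |
| 20 points | 0.5 SD | 29.3% | 5.7% |
| 30 points | 0.5 SD | 63.1% | 4.8% |

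Across all settings the stratified tests stayed between 4.0% and 6.1%.

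**The case against.** **No UK data are shown.** The documents give no UK nerve mix, cause mix, symptom level or outcome rate, and both datasets used the same criteria and period. A reader might infer that centre differences will surface as effects of nerve or cause. The documents do not support that: bias needs centre to be related to both grouping and endpoint, and nothing in them shows that it is. This objection stands, and the point is limited to a possible bias.

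**Much of the plan is not exposed.** Section 5 says the tests "will be used to compare in a univariable setting the primary and secondary endpoints between groups", and a reader might infer that the primary endpoints are at risk. They are not: costs, productivity loss and medication use come from Leuven records only (sections 2.1 and 7). So does EQ5D, and section 2.3 describes the other questionnaires as those used in the Leuven department. The permanent/temporary question has a logistic model that carries centre and a country check on merged data. This covers secondary endpoint 1 and, in substance, the comparison of symptoms between temporary and permanent injury. All of this stands.

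**The tests are labelled univariable, and the plan urges caution.** They are crude by design and omit age and sex as well. Section 5 also says that an isolated significant result will be read cautiously. That caution is tied to the number of analyses. Confounding by centre is systematic: it can move several endpoints together, and it becomes easier to detect as significant when datasets are pooled. This objection does not remove the gap.

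**Replacing every Fisher test with an asymptotic stratified test would be a mistake.** Some cause groups are small; endodontic injuries were 3 of 53 in the earlier Leuven cohort. This stands and shapes the fix.

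**Conclusion.** The gap is real but limited. On merged data, comparisons of symptoms, pain descriptors, sensory-test parameters, imaging and treatment by cause and nerve branch have no centre-adjusted analysis named, so they may be confounded by centre.

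The size cannot be fixed from the documents. Under the simulation assumptions, the false-positive rate is about 5% when only one of case mix and endpoint level differs, and 5.9% with small differences in both. It is about 22-30% with a 20-point mix difference plus a 20-point or 0.5 SD endpoint difference. Larger assumed differences give more. These figures rest on assumed UK values, a two-sided 5% level and no true effect within either centre. They show what could happen and do not predict what these data will show.

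The point is worth acting on because the remedy extends the plan's own approach to centre at little cost. It does not bear on the primary endpoints.

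**What to change.** In section 5, add that every comparison made on merged data takes account of centre, by one of two routes:

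- a centre-stratified test: van Elteren for two groups, stratified Kruskal-Wallis for more, Cochran-Mantel-Haenszel for categorical endpoints (its exact version where cells are sparse), and within-centre or partial Spearman correlations; or
- a regression for that endpoint with centre as a fixed effect.

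Also report a table of nerve, cause and outcome by centre, and give per-centre results beside each merged result. The table shows whether the conditions for confounding are present. The per-centre results show whether a combined test is hiding relations that differ between countries.

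No new data are needed. The cost is a sentence or two in the plan, slightly more analysis work, and a small loss of precision where strata are sparse. If the centres prove alike, the results should change little.

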2.2 Primary endpoints

- 1. What is the difference in total healthcare costs per patient and in total in patients with iatrogenic trigeminal nerve injury seen in our department according to cause of injury, injured nerve and outcome (temporary or permanent injury)?
 - A temporary injury will be defined as an injury that completely recovered with no more symptoms and clinical exam parameters within the normal limits during one of the consultations during the follow up period.
 - Permanent injury will be defined as an injury where no significant improvement in symptoms or clinical exam parameters was seen during one of the consultations during the follow up period.
- 2. What is the average productivity loss in days in patients with iatrogenic trigeminal nerve injury seen in our department according to cause of injury, injured nerve and outcome (temporary or permanent injury)?
- 3. Amount of medication use per medication class per patient in patients with iatrogenic trigeminal nerve injury seen in our department according to cause of injury, injured nerve and outcome (temporary or permanent injury)?

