2.3 Secondary endpoints

- 1. Are symptoms or clinical exam parameters (2 pointdiscrimination, directional sense, light touch, percentage of dermatome affected, pinprick threshold), MRCS classification and Sunderland classification predictive of a temporary or permanent injury? If so, which parameters can be withheld?
- 2. When an injury is present we will evaluate following parameters according to cause of injury, injured nerve branch and between temporary or permanent injury
 - Demographic data: age, gender
 - Symptoms, pain descriptors, interference with lifestyle
 - Clinical exam parameters (quantitative sensory testing)
 - Outcome & Follow-up: IHS criteria, surgical repair, use of medication
 - Social reimbursement rate and professional status
- 3. If data is present in the patient file regarding legal action taken by the patient against the caregiver who caused the injury this will be registered. We will evaluate how many patients undertook legal action and if they received compensation.
- 4. If sufficient follow up data is present, we will evaluate how long symptoms are present in case of a temporary injury and evaluate evolution of symptoms in relation to time.
- 5. Was imaging performed in light of the injury? If yes, what imaging modality was used (conebeam CT, CT, MRI, orthopantomogram) and did this influence treatment decisions?

- When looking at questionnaires applied in our department: are the results from the
 questionnaires comparable between the different causes of nerve injury, different affected
 branches? Are results comparable between patients suffering from a temporary or
 permanent injury? Following internationally validated questionnaires are part of routine
 examination of pain patients in our department and may be present in the patient KWS
 record:
 - McGill Pain Questionnaire
 - CPAQ-A
 - Brief Pain Inventory
 - EQ-5D
 - GAD-7
 - GCPS,
 - IES-DVL
 - OHIP-49
 - PainDetect
 - PHQ-9
 - PHQ-15
 - PSEQ
 - CPSI
 - IES
 - West Have-Yale Multidimensional Pain Questionnaire
 - Central sensitization inventory
- Is there a correlation between quality of life measured with EQ5D questionnaire and cause of injury, temporary versus permanent injuries, healthcare costs, productivity loss or medication use?

3. Selection and withdrawal of subjects

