The CastorEDC (www.castoredc.com) platform will be used to ensure a systematic approach towards entering datapoints after accessing the patient record in KWS. After reading the patient record in KWS, all data will be coded immediately in the CastorEDC database by creating a new and unique identifier, the study ID. A separate patient ID Log file will be kept on a secured UZ Leuven server containing the study ID and patient EAD. After completion of patient inclusion all data entered in CastorEDC will be exported to a coded SPSS database for further statistical analysis without names, initials, date of births, EAD or EMD numbers. The dataset will be password protected and stored on the UZ Leuven server while the study is in progress. Afterwards the study will be deleted from the Castor platform. The password protected SPSS dataset will be stored on the UZ Leuven server for

future research purposes or audits for the next 20 years. The database with research results does not relate to elements such as names, initials, and complete date of birth (dd /mm/yyyy).

Data from the already conducted retrospective study by prof. [name], will be delivered in a secured and coded SPSS dataset without names, initials, or dates of birth and will be manually imported in the CastorEDC platform using separate study specific ID's to allow data merging in 1 CRF platform: CastorEDC. This will allow to conduct retrospective analysis on a larger sample size.

7. Analysis of Healthcare Costs, Productivity Loss, Medication Use

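### No order of abstraction or masking is described for the Leuven records, so judged predictors in secondary endpoint 1 may be coded with the outcome known

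*Combined protocol and SAP*

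**What the plan says.** Section 6 (Data Management) describes how the Leuven records are handled: "After reading the patient record in KWS, all data will be coded immediately in the CastorEDC database". The rest of that sentence and the lines after it deal with the study ID, the ID log and the removal of identifiers.

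Secondary endpoint 1 (section 2.3) asks whether symptoms, examination parameters, "MRCS classification and Sunderland classification predictive of a temporary or permanent injury". Section 5 plans logistic regression, possibly multivariable, for this classification.

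Section 2.2 defines the outcome from follow-up visits. A temporary injury is "an injury that completely recovered with no more symptoms and clinical exam parameters within the normal limits during one of the consultations". A permanent injury is one where "no significant improvement in symptoms or clinical exam parameters was seen during one of the consultations during the follow up period".

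Section 3 expects about 400 subjects from Leuven, and "Another 900 subjects are estimated to be included from the retrospective dataset". Section 6 says that this second dataset arrives already coded. Section 2.1 assigns presentation, symptoms, clinical examination and outcome to the merged data, so endpoint 1 most naturally belongs there.

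The available text mentions no masked abstractor, no predictor-first entry, no second reader, no rule tying predictors to the first visit, and no field showing whether a grade was copied or assigned. The CRF (Addendum 1) is a separate file and could not be checked.

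**The concern.** Predictors and outcome sit in the same record, and entry follows reading. If the person coding a presenting symptom or a grade has already seen the follow-up notes, an ambiguous description may be read as more severe when the injury is known to have persisted. Coding that differs by known outcome can create or inflate an association with permanence, and endpoint 1 would report that as prediction.

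This is separate from two other features of the plan: the outcome is defined by the same kinds of variable that are offered as predictors, and no time point separates them. Fixing the predictors to the first visit would deal with those features. It would not deal with this one, because a first-visit note can still be interpreted in the light of how the case ended.

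The planned safeguards do not address it. Caution over a single significant p-value concerns multiplicity, whereas outcome-aware coding could shift several judged predictors in the same direction. Multiple imputation concerns missing values.

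**Working it through.** The plan gives no figure for this point. The 400 and 900 are estimates of available records, with no power calculation behind them, so there is nothing to reproduce. What follows is illustration under stated assumptions.

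**Inputs from the documents.** 400 Leuven records and 900 others (section 3), so the Leuven share is 400/1300 = 0.308. Significance level 0.05 (section 5; two-sided assumed, as sidedness is not stated). The background section reports 60% persistent disturbance in the earlier 53-case series; 50% to 60% permanent is used in illustration B.

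**Illustration A: upgrading of permanent cases only.** Assumed: 40% are severe in both outcome groups (true OR 1.00), and a fraction u of non-severe permanent cases is graded up.

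Observed proportion severe among permanent cases = 0.40 + 0.60u. Odds among temporary cases = 0.40/0.60 = 0.667.

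| u | Proportion | Odds | OR, Leuven |
|---|---|---|---|
| 5% | 0.43 | 0.754 | 1.13 |
| 10% | 0.46 | 0.852 | 1.28 |
| 20% | 0.52 | 1.083 | 1.63 |

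For the merged set, assume that the other 900 records are unaffected and that prevalence and outcome mix are equal in the two datasets. The proportion becomes 0.40 + 0.308 × 0.60u:

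| u | Proportion | Odds | OR, merged |
|---|---|---|---|
| 5% | 0.409 | 0.693 | 1.04 |
| 10% | 0.418 | 0.720 | 1.08 |
| 20% | 0.437 | 0.776 | 1.16 |

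**Illustration B: coding shifted in both directions.** Assumed: true prevalence q of 30% or 50% in both groups. A fraction e of non-severe permanent cases is graded up, and the same fraction of severe temporary cases is graded down. Then p1 = q + e(1 − q) and p2 = q(1 − e). For the merged set, each shift from q is multiplied by 0.308. The chance of p < 0.05 comes from the normal approximation for two proportions: with d = |p1 − p2|, it is Φ((d − z·s0)/s1) + Φ((−d − z·s0)/s1), where s0 is the pooled and s1 the unpooled standard error.

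Example, N = 400, half permanent, q = 0.30, e = 5%: p1 = 0.335, p2 = 0.285, OR = (0.335/0.665)/(0.285/0.715) = 1.26, chance of p < 0.05 = 0.19.

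| e | OR, Leuven (400) | False-positive rate | OR, merged (1300) | False-positive rate |
|---|---|---|---|---|
| 0 | 1.00 | 0.05 | 1.00 | 0.05 |
| 2% | 1.08–1.10 | about 0.07 | 1.02–1.03 | about 0.06 |
| 5% | 1.22–1.26 | 0.17–0.19 | 1.06–1.08 | 0.08–0.09 |
| 10% | 1.49–1.59 | 0.50–0.57 | 1.13–1.16 | 0.19–0.23 |

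No document gives u or e. At zero there is no distortion, at 2% it is small, and at 10% it would matter even after dilution.

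**The case against.** The strongest reply is that the quoted sentence is mainly about pseudonymisation. A reader might infer that the whole record is read before any field is entered. The text does not say so, and the CRF may settle the order of entry. That stands, and it is why the point concerns a safeguard that is not described rather than a stated faulty procedure.

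A reader might also infer that the abstractor assigns the MRCS and Sunderland grades. The documents do not say whether these are assigned or copied from the clinician's note. Section 2.3 elsewhere labels the examination parameters as quantitative sensory testing, and values transcribed from a dated examination leave little room for this bias. Cause of injury is read from the same record, but it is not among the endpoint 1 predictors. These replies stand and narrow the point to judged fields.

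The sentence covers only about 400 of 1300 records, or 31%. That stands. How the other records were abstracted is not described, so treating them as unaffected is an assumption.

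It could be said that the problem would come to light anyway. The ID log and access to source data would allow a masked re-abstraction of a sample, so it would be wrong to call the bias undetectable. But no such check is planned. The planned test of country dependence might show a Leuven-only distortion, yet could not tell it from a real difference between centres.

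Finally, the average referral delay in the earlier series was 10 months, with a maximum of 6.5 years. A first-visit note can itself reveal persistence, so entering it first protects only in part. That stands as a limit on the remedy.

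**Conclusion.** The point holds as a risk. For the Leuven records, the described workflow leaves room for judged predictors to be coded with the outcome known, and the available text contains nothing to prevent it. Saying that the workflow builds in an association would go too far: whether bias arises, and how large it is, depends on coding behaviour on which the documents are silent.

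Under illustration A, a null association would appear as an OR of 1.13 to 1.63 in the Leuven records and about 1.04 to 1.16 in the merged set. These figures rest on the assumed 40% prevalence, upgrading of 5% to 20%, an equal outcome mix and an unaffected second dataset. The point bears on one secondary endpoint. Cost, productivity and medication data come from the sickness fund's own records and are not coded by this route, although the permanent/temporary grouping used with them does come from the hospital record. A cheap improvement is warranted; the plan does not fail on this point.

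**What to change.** If the CRF already enforces an order of entry, one sentence in section 6 saying so settles the order. Otherwise:

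1. For records not yet entered, complete and lock the first-consultation form (symptoms, examination, MRCS, Sunderland) before opening later notes. Then enter follow-up and outcome.
2. Add a CRF field marking each grade as recorded by the clinician at the visit or derived by the abstractor.
3. Repeat secondary endpoint 1 on clinician-recorded values for the Leuven records, and for the second dataset only if the source of its grades is known. State in the protocol how that dataset was abstracted, or that this is unknown.

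The cost is one data-entry instruction, one added field, a repeat analysis and slightly slower entry. No extra reader is needed. The order of entry cannot help records already coded, and it protects only partly where a late-referred patient's first note already shows persistence. Both limits should be reported with the result.
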